A Pilot Study Testing Benefits of Ursolic Acid (UA) as a Countermeasure To Myopenia and Insulin Resistance in Chronic SCI

3. Objectives

To address the need for an agent that maintains muscle mass and attenuates IR after SCI, we propose a 'first-in-humans with SCI' pilot trial that tests benefits of UA as a countermeasure to sarcopenia and IR.

Aim 1

• To explore effects of UA administration on upper extremity lean mass and peak strength in persons with paraplegia.

Aim 2

• To test effects of UA administration in sedentary individuals with tetraplegia on whole body resting insulin sensitivity, glucose/insulin/inflammatory responses to an oral glucose challenge (OGTT), and whole-body lean mass.

4. Study Endpoints

Primary Outcome Measure(s):

- Change in Muscle Mass Using Dual X-ray Absorptiometry (DXA)

 Time Frame: Baseline, 12 weeks
- 2. Change in Peak Isokinetic Strength
 - a. Time Frame: Baseline, 12 weeks
- Changes in Fasting Insulin Resistance (IR)
 a. Time Frame: Baseline, 12 weeks
- 4. Changes in Glucose Disposal
 a. Time Frame: Baseline, 12 weeks

5. Background

The multi-year COVID-19 pandemic has resulted in a decline of overall physical activity, life-satisfaction, and health within the spinal cord injured (SCI) community.¹ **During the pandemic, people with SCI have experienced health decay to a far greater extent than the general population, primarily due to profound social distancing, fears of social engagement and infection, and restrictions in exercise engagement.² Even without social isolation and exercise restrictions, trauma to the spinal cord is typically associated with physical and metabolic disorders that have wide-ranging effects on almost all body systems.³ Our works,⁴ and the works of other investigators⁵ have reported a level-of-injury dependent myopenia – i.e.,** *clinically relevant muscle wasting* **– which is commonly observed following spinal cord injury (SCI), and ultimately compromises post-SCI function, metabolism, body composition, and health. Adjustments to body composition that accompany SCI-related myopenia include a decline of metabolically active muscle mass accompanying the loss of actively contracting muscle, which reduces whole body caloric expenditure and establishes**

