In a pre-clinical study,⁹ we investigated UA as an agent affecting anabolic, metabolically-linked signaling pathways in muscle, and explored phenotypic outcomes in sublesional muscle following traumatic SCI. Our primary objectives were to examine following experimental SCI i. intracellular mTOR signaling, ii. The expression of related catabolic genes, and iii. The effects on these outcomes with UA treatment. We hypothesize that SCI would i. reduce growth pathways via mTOR signaling, ii. Increase the expression of catabolic genes, and iii. UA will attenuate these SCI-induced changes. In addition, we examined the effect of SCI on physical and functional measures, and whether UA-promoted signaling in muscle translated to improvements in these outcome measures. When examining effects of UA treatment on sublesional muscle mTOR signaling, catabolic genes, and functional deficits following severe SCI in mice we observed that UA treatment significantly attenuated SCI-induced decreases in activated forms of mTOR, and signaling intermediates PI3K, AKT, and S6K, and the upregulation of catabolic genes including FOXO1, MAFbx, MURF-1, and PSMD11. In addition, UA treatment improved SCI-induced deficits in body and sublesional muscle mass, as well as functional outcomes related to muscle function, motor coordination, and strength.

These findings provided first evidence that UA treatment may be a potential therapeutic strategy to improve muscle specific pathological consequences of SCI.

6. Inclusion and Exclusion Criteria

Inclusion Criteria

- 18-65 years of age
- Aim 1: Male and female individuals with paraplegia having chronic (≥ 1 year) complete and incomplete (AIS A/B/C) injuries from T2-T8
- Aim 2: Male and female individuals wi4.th chronic (≥ 1 year) complete and incomplete (AIS A/B/C) injuries from C4-C7

Exclusion Criteria

- Pregnant or planning to become pregnant
- Women who are breastfeeding

Number of Subjects

- Aim 1 will enroll up to 10 participants
- Aim 2 will enroll up to 10 participants

7. Study Recruitment Methods

Recruitment will include IRB-approved flyers posted throughout the Christine E. Lynn Rehabilitation Center for the Miami Project to Cure Paralysis; social media; word-of-mouth at the Christine E. Lynn Rehabilitation Center for the Miami Project to Cure Paralysis; online advertisement using IRB-approved language from flyers, telephone or email contact for those individuals who have previously consented for contact in other studies.

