In addition, we will utilize the Miami Project to Cure Paralysis research registry of >3000 individuals with SCI who have expressed an interest in participating in research studies. The registry currently is composed mainly of individuals with traumatic SCI (89%) who are \geq 18 years old. It includes men and women of different ages with SCI that differs by level, severity, duration, and cause. These individuals have completed and submitted a form that outlines their medical history. Their level of SCI and degree of completeness has also been evaluated. This registry often provides adequate subject enrollment for studies without the inherent expense and difficulty of coordinating recruitment at multiple sites.

8. Study Timelines

Participants that are eligible for Aim 1 will come to the research site (Miami Project) a total of up to 38 visits:

- One day for consenting and screening assessments; Screening assessments may be completed on 2 separate visits to accommodate scheduling conflicts. This will add an additional day to the total visits
- 3 times a week for 12 weeks for exercise intervention;
- one day for post-study assessments.

During this time, they will:

- Take an oral 400mg (8 capsules 4 in the morning/200mg and 4 at night/200mg) supplement of UA every day for 12 weeks.
- Drug accountability will occur every month and study staff will dispense 2 bottle every month and collect all used or empty bottles
- Pregnancy tests will occur monthly for females of child-bearing potential
- Take part in an exercise program where you will perform strength-training exercises on one arm, 3 times a week, for 12 weeks.
- Complete pre and post intervention assessments (see section 8)

Participants that are eligible for Aim 2 will come to the research site (Miami Project) up to 4 visits:

- One day for consenting and screening assessments. On this visit they will receive the first 2 bottles of the UA.
- 2 monthly visits for drug accountability where study staff will dispense 2 bottles every month and collect used or empty bottles; monthly pregnancy tests for females of child-bearing potential
- One day for post study assessments

During this time, they will:

- Take an oral 400mg (8 capsules 4 in the morning/200mg and 4 at night/200mg) supplement of UA every day for 12 weeks
- Complete pre and post intervention assessments (see section 8)

9. Product and Procedures

Ursolic Acid (UA)

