UA will be sourced as Biotech Nutritions Ursolic Acid Gelatin Free Non-GMO capsules (i.e. form) ; 200mg (4 total capsules, 50mg each) taken twice daily by mouth with food and a non-alcohol-containing drink. UA is a non-Rx nutraceutical obtained without prescription. We will neither claim an FDA 'brand' for the product, nor propose a new or extended indication for its use.

Manufacturer: Biotech Nutritions [name] Ph: [name]

- Aim 1: will couple UA administration at doses that increase muscle mass with strengthening exercise performed in one arm only.
 - Subjects will receive 2 bottles of oral UA every month. Subjects will be asked to take 400 mg or 8 capsules (4 in the morning/200mg and 4 at night/ 200mg) daily for 12-weeks
 - Adherence to the UA intervention will be done once a month by study staff and will entail:
 - collection of used bottle(s)
 - counting remaining capsules, if any
 - calculation of compliance: [(days x 8) capsules remaining
 - and dispensing a new bottle(s).

**Education regarding the importance of compliance to the dosing requirements will be part of the monthly drug accountability.

*** Research Studies Subjects will be offered participation in other PM&R and Miami Project to Cure Paralysis studies for which they may be eligible. The possibility of dual enrollment or partial overlap of participation in more than one study is conceivable. This could result in duplication of required assessments subjects would need to complete. However, to simplify participation, reduce the number of visits to our research lab, and mitigate testing redundancy, we may apply test results completed for one study to another in those cases.

- During this period, one upper limb (only), randomized by selection, will undergo exercise conditioning three times weekly using a strengthening program we have established to increase muscle mass and strength in people with SCI. The other arm will remain untrained as a control receiving the same whole body dose of UA.
- Lean mass will be examined before and after 12 weeks of treatment using dual-ray absorptiometry (DXA) and non-contrast CT scan of both arms, with the area of interest identified from the glenohumeral joint distally to the ulnar styloid.
- Peak isokinetic strength of both arms at 90 degrees of flexion will be tested in elbow flexion and extension on a Biodex dynamometer.
- Maximal inspiratory pressure will be measured with the Pro2 Fit device.

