The co-primary outcomes will be lean mass and peak strength.

- Aim 2 subjects will:
 - Subjects will receive 2 bottles of oral UA every month
 - Subjects will be asked to take 400 mg or 8 capsules (4 in the morning/200mg and 4 at night/ 200mg) daily for 12-weeks.
 - Adherence to the UA intervention will be done once a month by study staff and will entail:
 - collection of used bottle
 - counting remaining capsules, if any
 - calculation of compliance: [(days x 8) capsules remaining]
 - and dispensing a new bottles.

**Education regarding the importance of compliance to the dosing requirements will be part of the monthly drug accountability.

*** Research Studies Subjects will be offered participation in other PM&R and Miami Project to Cure Paralysis studies for which they may be eligible. The possibility of dual enrollment or partial overlap of participation in more than one study is conceivable. This could result in duplication of required assessments subjects would need to complete. However, to simplify participation, reduce the number of visits to our research lab, and mitigate testing redundancy, we may apply test results completed for one study to another in those cases.

- Whole body lean mass will be determined by DXA and CT scan before and after 12 weeks of treatment.
- Before and after the 12-week UA intervention an oral glucose tolerance test (OGTT: 75 g glucose as TrutolTM) will be administrated following an overnight fast.
 - Bloods taken before glucose ingestion will be analyzed for glucose, insulin, and inflammatory biomarkers (TNF-alpha, IL-6, and CRP).
 - Bloods will also be taken at 30-minute intervals for two hours.
- Maximal inspiratory pressure will be measured with the Pro2 Fit device.

Co-primary outcomes will be the fasting IR determined by the HOMA v2 model and the rates of glucose disposal defined by the area under the glucose challenge curve (AUC).

Dual X-ray Absorptiometry (DXA)*

The regional composition for Fat Free Mass (FFM), Fat Mass (FM), % FM, and Lean Mass (LM), in regions of interest including the trunk, arms, android, and gynoid regions will be measured by DXA as described by Gorgey et al., Spinal Cord 2018. Body composition will be measured by whole body scans using a GE

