Subjects may withdraw from the study without prejudice to medical treatment at the center or involvement in future studies at the discretion of the PI. The ICF advises students and employees of the rights with respect to study withdrawal. We may end a subject's participation in the study if s/he experiences adverse effects or in case of an incidental pregnancy. Subjects who experience AEs (nausea, bloating, for example) will be referred to the Study Physician for appropriate medical care and will have their dose decreased by 25% (total dose of 300mg or 3 capsulse in the morning plus 3 capsules at night). This lower dose has been reported to be efficacious and may help alleviate the AEs. If symptoms do not improve after 1-2 days, subjects will be withdrawn from the study. Subjects that become upset by answering questions about their SCI will be referred to the Study Physician for appropriate medical care. Compliance to UA dosing will be calculated monthly and subjects who fall below the 80% adherence threshold will be withdrawn from the study.

Risks to Subjects

- Subjects may become upset by having an investigator ask questions about their SCI.
- The risks of blood drawing include fainting, the occurrence of temporary discomfort and/or bruise at the site of puncture; rarely, infection or the formation of a small clot or swelling to the vein and surrounding area may occur. There may be slight discomfort in the arm or hand during the venipuncture. Occasionally, a small accumulation of blood (hematoma) may form at the point of insertion of the needle. This may result in a small lump that will disappear. Occasionally, a small amount of bleeding may occur around the catheter site. On rare occasions, a local infection may occur around the venipuncture site.
- You may find yourself becoming hungry when you fast to have your blood drawn.
- Answering questions about your injury may make you feel nervous or upset. If you do not wish to answer a question, you can skip it and go to the next question.
- DXA scans may cause anxiety and additional radiation exposure. Radiation exposure is less than two weeks of natural background radiation or like the exposure during a round-trip cross-country flight.
- CT Imaging may cause anxiety and an excess exposure to radiation. Exposure to low-levels of radiation does not cause immediate health effects, but can cause a small increase in the risk of cancer over a lifetime.

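### A participant who takes every capsule of the reduced dose scores 75% on a compliance measure fixed at 8 capsules a day, below the 80% withdrawal threshold

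*Combined protocol and SAP*

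**What the plan says.** Section 9 (Product and Procedures) gives the compliance calculation once for each aim. In Aim 1 it is printed as "calculation of compliance: [(days x 8) capsules remaining", and the Aim 2 version differs only by a closing bracket. The 8 is the full daily count: 4 capsules of 50 mg twice a day, 400 mg in all. On supply, section 9 says "Subjects will receive 2 bottles of oral UA every month". It does not give the number of capsules in a bottle.

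Section 13 (Withdrawal of Subjects) says that participants with adverse events such as nausea or bloating "will have their dose decreased by 25% (total dose of 300mg or 3 capsulse in the morning plus 3 capsules at night"). It describes this lower dose as reported to be efficacious. It continues: "If symptoms do not improve after 1-2 days, subjects will be withdrawn from the study". Those who do improve are therefore meant to carry on. The paragraph ends with the adherence rule: "Compliance to UA dosing will be calculated monthly and subjects who fall below the 80% adherence threshold will be withdrawn from the study".

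Section 4 gives every primary outcome as a change with "Time Frame: Baseline, 12 weeks". Section 6 sets the size: "Aim 1 will enroll up to 10 participants", and the same number for Aim 2.

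**The concern.** The two rules in section 13 appear to work against each other. One keeps a participant in the trial on 6 capsules a day. The other may remove the same participant for not taking enough, because the compliance count in section 9 still expects 8. Both are written as mandatory.

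At stake is the 12-week outcome of anyone caught this way. Baseline and other data already collected would remain, but a participant withdrawn at an interim monthly check would probably not reach the post-study assessment and so would have no 12-week change. In an aim of up to 10 people, that is at least a tenth of the primary data for each person lost. The loss would also be selective, since it can fall only on people who had an adverse event and whose symptoms eased on the lower dose.

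**Working it through.** **Inputs.** Full dose 8 capsules a day and capsule strength 50 mg (section 9). Reduced dose 6 a day and threshold 80% (section 13). Month length is not defined, so 28 and 30 days are both shown.

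**The plan's own figure.** 400 mg x 0.75 = 300 mg = 6 x 50 mg. The stated reduced dose is correct.

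**Reading A: capsules taken / (days x 8).** For a month of M days wholly at the reduced dose:

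- Score = 6M / 8M = 75.0% for any M: 168/224 for 28 days, 180/240 for 30 days.
- Passing needs 0.8 x 8 = 6.4 capsules a day, more than the 6 prescribed. Over 28 days, 0.8 x 224 = 179.2, so 180 capsules are needed against 168 prescribed, 12 too few.
- A full-dose participant passes with 180/224 = 80.4%, having missed 224 - 180 = 44 capsules.

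**Mixed months.** With r days at the reduced dose and no capsule missed, score = (8M - 2r) / 8M. This is at least 80% only when r is at most 0.8M.

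| Month | Reduced-dose days | Score | Result |
|---|---|---|---|
| 28 days | 22 | 180/224 = 80.4% | stays |
| 28 days | 23 | 178/224 = 79.5% | withdrawn |
| 30 days | 24 | 192/240 = 80.0% | stays |
| 30 days | 25 | 190/240 = 79.2% | withdrawn |

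**Timing.** Section 8 places two monthly accountability visits before the post-study visit in Aim 2. Assume 28-day intervals and a reduction that continues to the end.

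- A start by day 6 gives at least 23 reduced days in the first interval and fails the first check.
- A start on days 7 to 34 fails the second check. Day 34 to day 56 is exactly 23 days.
- A start on day 35 leaves 22 reduced days in the second interval, so that check is passed. A start on day 35 or later can fail only at the end-of-treatment count, where the 12-week assessment would probably be obtained anyway.

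**Reading B: (days x 8 - capsules remaining) / (days x 8).** This is the other natural completion, and it depends on the supply S. After M perfect reduced-dose days, S - 6M capsules remain, so score = (14M - S) / 8M. For 28 days:

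- S = 224 (exactly a full-dose supply): 168/224 = 75.0%.
- S = 240 (assumed): 152/224 = 67.9%.
- A score of 80% requires S of 212 or less. For 30 days the limit is 228.

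Both limits lie below a full-dose month's supply (224 and 240). On this reading too, 75% is the ceiling whenever enough is dispensed to cover the full dose, and nothing found in the text reduces the supply after a dose cut.

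**The case against.** The strongest reply is that the failing formula is a reconstruction. The printed expression has no operator, divisor or percentage sign, and a symbol may have been lost when the text was extracted. That stands, and the result is conditional on how the gap is filled. But the 8 is legible in both places, and both natural completions give at most 75% when a full-dose supply is dispensed.

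A second reply is that section 9 speaks of complying with the dosing requirements, and a reduced participant's requirement is 6 a day. The 8 may be only the standard regimen's count, and an author who calls the lower dose efficacious can hardly have meant that taking all of it is non-adherence. That is probably the intention, and staff may well apply it. The text does not say so, however, and a mandatory withdrawal rule should not rely on staff departing from the only formula given. The statement that nothing changes the 8 has one limit: the text between the risk list in section 13 and section 16 was not available for this review.

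A third reply is that the consequence needs several steps: an adverse event, improvement within a day or two, a reduction lasting most of a month, an interim rather than a final check, and withdrawal that forfeits the last assessment. The documents give no adverse event rate and no duration for the reduction. All of this stands and limits the severity. It is also true that investigators may already end participation for adverse effects, so some loss of this kind is built into the design. That power is discretionary, whereas the 80% rule is not.

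Finally, no printed figure is miscalculated. That is correct. The fault is that two rules conflict when followed as written.

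**Conclusion.** The concern holds, at minor severity. If the incomplete formula means capsules taken / (days x 8), a fully adherent month at the reduced dose scores 75.0% and triggers withdrawal. So does any month with at least 23 of 28, or 25 of 30, days at the reduced dose. If it means the expected count less the capsules remaining, the same conclusion follows whenever the supply covers the full dose; bottle size is not stated. A lost 12-week outcome further requires that the failure comes at an interim check and that withdrawal ends follow-up, which is likely but not stated. How many participants would be affected cannot be estimated from the documents.

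**What to change.** In section 9 (both aims), define compliance as 100 x capsules taken / capsules prescribed in the interval at the dose in force for that participant. In section 13, state that the 80% rule applies to that figure.

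A perfect reduced-dose month of 28 days then scores 168/168 = 100%, and the threshold falls at 135 capsules (135/168 = 80.4%; 134/168 = 79.8%). For a 28-day month with 14 days at each dose, the denominator is 8 x 14 + 6 x 14 = 196. The doses and the 80% level do not change.

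The cost is one formula in two places and one phrase in section 13. Capsules are already counted monthly. Staff would also need the date of any dose reduction and the number of capsules dispensed. The same edit completes the unfinished formula.

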- [name]: He is in charge of the lifestyle center at LRC. He will assist with the exercise intervention.

16. Compensation for Research-Related Injury

Details regarding research related injury compensation will be included in the FE agreement. The following language was added to the ICF: You may be exposed to risk of injury from participation in this study. If injury occurs, treatment will in most cases be available. If you have insurance, your insurance company may or may not pay for these costs. If you do not have insurance, or if your insurance company refuses to pay, you will be expected to pay. Funds to compensate for

pain, expenses, lost wages and other damages caused by injury are not routinely available.

17. Economic Burden to Subjects

Subjects that sign consent and are eligible to participate will be reimbursed by check (sent by mail) after each completed visit.

Group 1 (total \$200):

- \$50 for completing the first or screening visit
- \$150 (\$50 every month) for completing the 12-week intervention (exercise and daily UA).
- Re-dispensing of a new UA bottle will occur once a month at a scheduled visit
- Monthly pregnancy tests for all women of child-bearing potential
- \$50 for completing the post-study assessments at the final visit

Group 2(total \$200):

- \$50 for completing the first or screening visit
- \$150 (\$50 every month) for completing the 12 week intervention (daily UA)
- Subjects will be required to return to the study site once a month for redispensing of the UA.
- Monthly pregnancy tests for all women of child-bearing potential
- \$50 for completing the post-study assessments at the final visit

18. Consent Process

Consent will take place at each Center in a private office at the Miami Project to Cure Paralysis located at LRC, 2nd Floor. We will abide all regulatory mandates and suggestions of the FDA 'A Guide to Informed Consent - Information Sheet' www.fda.gov/RegulatoryInformation/Guidances/ucm126431.htm

Before signing the ICF study subject candidates will be encouraged to share the ICF with family, a trusted family friend or their physician. Subject candidates will be required to read the approved consent form. The person obtaining consent will ask several questions to assure they understand the study procedures and risks. A statement on the consent form will advise university employees that their participation (or failure to participate) will not affect their employment or academic status. The statement in the consent will advise individuals with spinal cord injury that their participation (or decision to not participate) will not influence their treatment or candidacy for other studies in any way. Individuals will be given the right to withdraw at any time without prejudice.

Process to Document Consent in Writing

- Subjects will be presented with and asked to review the consent form. They will be queried whether they have any questions and if so, these questions will be addressed by the principal investigator or individual approved to obtain consent. Once the consent form is signed (subject may provide a mark if unable to sign), witnessed, and signed by the principal investigator (or other designated person obtaining consent) a copy of the consent will be provided so that the subject can review their rights.
- A copy of the consent will be provided so that the subject can review their rights at any time in future. The original copy of the ICF will be placed in the participant file and secured as described in section 21.b

Authorization for Use and Disclosure of Protected Health Information (HIPAA)

Waiver of Authorization for access to medical record for subject identification/recruitment.

19. REFERENCES:

- McMillan, David W., et al. "Virtual Strategies for the Broad Delivery of High Intensity Exercise in Persons With Spinal Cord Injury: Ongoing Studies and Considerations for Implementation." Frontiers in Sports and Active Living (2021): 214.
- 2. de Groot, Sonja, and Rachel E. Cowan. "Exercise for people with SCI: so important but difficult to achieve." Spinal Cord 59.1 (2021): 1-2.
